6.4 Minimization of Bias

Selection of subjects, treatment of subjects, and evaluation of study data are potential sources of bias. Methods incorporated in the study design to minimize potential bias include (but are not limited to):

- Subjects will be screened to confirm eligibility for enrollment with defined inclusion/exclusion criteria prior to enrollment.
- Subjects will be selected randomly (excluding the first enrolled subject at each center) for evaluating the incidence of [REDACTED] pulmonary vein stenosis.
- Demographics and medical history will be collected at baseline in order to later assess possible characteristics that may influence study endpoints.

- Data collection requirements and study procedures will be standardized across all study centers.
- No more than 15% (45) of ablated study subjects may come from a single center.
- No more than 33% (100) of ablated study subjects may come from geographies outside the US.
- All study center and Medtronic personnel will be trained using standardized training materials.
- All study clinicians will be trained on and required to follow the Clinical Investigation Plan.
- All study investigators will be required to meet the requirements of 21 CFR Part 54, Financial Disclosure by Clinical Investigators.
- Regular monitoring visits will be conducted to verify source data and adherence to the Clinical Investigation Plan and source data.
- A core laboratory will be used to characterize [REDACTED] all baseline and 6-month follow-up 48-hour ambulatory ECG monitors
- [REDACTED]
- A core laboratory will be used to evaluate CT or MRI images for pulmonary vein stenosis at baseline and at the 3-month post-procedure follow-up visit.
- An independent clinical events committee (CEC) will be utilized to regularly review and adjudicate reported adverse events.
- An independent data monitoring committee (DMC) will be utilized to review accumulating safety data, help safeguard the interests of study subjects, and monitor the overall conduct of the study

In summary, potential sources of bias that may be encountered in this clinical investigation have been considered and minimized by careful study design.

6.5 Subset Selection Randomization Process

Upon confirmation that all inclusion and no exclusion criteria have been met, the Patient Informed Consent has been signed, and baseline testing has been completed, a subject may be randomized using an electronic randomization system to [REDACTED] the PVS assessment cohort. It is recommended that randomization occur as close as possible but prior to the index Phased RF procedure to minimize study attrition following randomization.

Specifically, 100 subjects will be randomly selected from the first 200 enrolled subjects to participate in the PVS assessment cohort. The randomization schedule will not allow the first enrolled subject at a study center to be selected into the PVS assessment cohort.

[REDACTED]

The remaining subjects not randomly selected for participation in the PVS assessment cohort [REDACTED] will have no additional assessments performed.

A Medtronic statistician will create the randomization schedules and the randomization schedule will ensure that subjects cannot be randomized to [REDACTED] PVS assessment cohorts.

7. STUDY PROCEDURES

Center personnel training will be completed prior to participation in this clinical study. In addition, all participating center staff must be trained on the current version of the CIP and must be delegated by the principal investigator to perform study specific activities. Study materials will be provided to center staff prior to site initiation. The site neurologist must be certified in administering the National Institute of Health Stroke Scale (NIHSS) and the Modified Rankin Score (mRS). The site radiology staff (e.g. technicians) may be trained to the study required imaging parameters.

Medtronic personnel may provide technical support, including completion of a technical support sheet, during the ablation procedure.

7.1 Investigation sites

Sites must have an EP physician experienced in ablation of atrial fibrillation and trained by Medtronic personnel in the handling of the Phased RF System. Sites are also required to have a Neurologist (or equivalent physician with specialization in stroke diagnosis and treatment, e.g. British Association of Stroke Physicians (BASP) in the UK) and adequate infrastructure and diagnostics to comply with study required procedures.

A list of participating investigators and investigational sites will be submitted under a separate cover.

7.2 Site activation

During the activation process (prior to subject enrollment), Medtronic will train site personnel on the clinical investigation plan, relevant standards and regulations, informed consent, written clinical investigation agreements and on data collection and reporting tools. If new members join the investigational site team, they will receive training on the applicable clinical investigation requirements relevant to their role before contributing to the clinical investigation. Additionally, Medtronic will emphasize the importance of enrolling women in this study during the site training process. Medtronic will also work

with the sites to develop strategies to improve the participation of women in this study that may include, but are not limited to: tailored communication strategies, inclusion of health care practitioners to help with recruitment, monetary incentives, flexibility of follow up schedule, and reviewing screening logs to identify trends that are inhibiting enrollment of women.

Prior to performing study related activities, all local regulatory requirements shall be fulfilled, including, but not limited to the following: IRB/MEC approval of the current version of the CIP and Patient Informed Consent form, regulatory authority approval or notification as required per local law, fully executed Clinical Trial Agreement (CTA), Financial Disclosure, investigator Curriculum Vitae (CV), Delegated Task List (DTL) and documentation of study training. In addition, all participating site staff must be trained on the current version of the CIP and must be delegated by the principal investigator to perform study related activities. Medtronic will provide each study center with written documentation of study center/investigator readiness, this letter must be received prior to subject enrollment.

7.3 Equipment requirements

The following center-provided equipment must be available at each center to support study activities:

- E7506 Valley lab patient return electrodes (2 per subject ablation)
- MRI system [REDACTED]
- CT scanner
- ACT analyzer capable of providing measurements every 10 minutes*

*NOTE: ACT analyzer calibration records must be made available for sponsor review prior to each Phased RF ablation procedure.

7.4 Patient informed consent process

Patient informed consent is defined as legally effective, documented confirmation of a subject's (or their legally authorized representative or guardian) voluntary agreement to participate in a particular clinical study after information has been given to the subject on all aspects of the clinical study that are relevant to the subject's decision to participate. This process includes obtaining a Consent and a/an Authorization to Use and Disclose Personal Health Information/Research Authorization/other privacy language as required by law that has been approved by Competent Authorities (CA), the investigational center's Medical Ethics Committee (MEC), Institutional Review Board (IRB), or Head of Medical Institution and signed and dated by the subject (or their legally authorized representative or guardian). A subject may only consent after information has been given to the subject on all aspects of the clinical investigation that are relevant to the subject's decision to participate.

Prior to enrolling subjects, each investigational center's MEC, IRB, or Head of Medical Institution will be required to approve the Consent Form (CF), and Authorization to Use

and Disclose Personal Health Information/Research Authorization/other privacy language as required by law. The document(s) must be controlled (i.e. versioned and/or dated) to ensure it is clear which version(s) were approved by the (MEC) or (IRB), or Head of Medical Institution. Any adaptation of the sample Consent Form must be reviewed by Medtronic and the MEC or IRB, or Head of Medical Institution reviewing the application prior to enrolling subjects.

Prior to initiation of any study-specific procedures, patient informed consent must be obtained from the subject (or their legally authorized representative or guardian). Likewise, privacy or health information protection regulation in other geographies may require subjects to sign additional forms to authorize centers to submit subject information to the study sponsor. The Consent Form and Authorization to Use and Disclose Personal Health Information/Research Authorization/other privacy language as required by law must be given to the subject (or their legally authorized representative or guardian) in a language he/she is able to read and understand. The process of patient informed consent must not be conducted using coercion or undue improper influence on or inducement of the subject to participate by the investigator or other center personnel.

The process of obtaining patient informed consent shall:

- Not waive or appear to waive subject's legal rights
- Use language that is non-technical and understandable to the subject
- Provide ample time for the subject to read and understand the informed consent form and to ask questions, receive answers and consider participation
- Include a personally dated signature of the subject acknowledging that their participation in the study is voluntary
- EEA only: Include a personally dated signature by the principal investigator or authorized designee responsible for conducting the informed consent process

If the Consent Form is obtained the same day the subject begins participating in study-related procedures, it must be documented in the subject's case history that consent was obtained prior to participation in any study-related procedures. It is best practice for the informed consent process to be documented in the subject's case history, regardless of circumstance.

In the event a Legally Authorized Representative or guardian is utilized, copy of this legal delegation must be retained in the subject's records. In the event the subject cannot read and/or write, witnessed (impartial third party) patient informed consent will be allowed, provided detailed documentation of the process is recorded in the subject's case history and the witness signs and dates the patient informed consent. The subject should "make his mark" (sign or otherwise physically mark the document so as to indicate consent) on the ICF as well. The Consent Form should document the method used for communication with the prospective subject and the specific means by which the prospective subject communicated agreement to participate in the study.

The original or a copy of the signed Consent Form must be filed in the hospital/clinical chart and with the subject's study documents. A copy of the *signed and dated* Consent

Form and signed Authorization to Use and Disclose Personal Health Information/Research Authorization/other privacy language as required by law must be provided to the subject.

The Consent Form and Authorization to Use and Disclose Personal Health Information/Research Authorization/other privacy language as required by law must be available for monitoring and auditing.

Any changes to a previously approved Informed Consent Form throughout the course of the study must be approved by the MEC or IRB, or Head of Medical Institution reviewing the application before being used to consent a prospective study subject. The MEC or IRB, or Head of Medical Institution –approved Consent Form must also be submitted to Medtronic for review and approval. The document(s) must be controlled (i.e. versioned and/or dated) to ensure it is clear which version(s) were approved by the Medical Ethics Committee (MEC) or Institutional Review Board (IRB), or Head of Medical Institution. All important new information should be provided to new and existing subjects throughout the study. For existing subjects, the informed consent process as described above needs to be repeated for significant changes as determined by the MEC, IRB or Head of Medical Institution.

7.5 Data collection

Clinical data is collected at designated time points throughout the study. Data will be collected using an electronic data management system for clinical studies. Data will be stored in a secure, password-protected database which will be backed up nightly. Data will be reviewed using programmed and manual data checks. Data queries will be made available to study centers for resolution. Study management reports may be generated by Medtronic to monitor data quality and study progress. At the end of the study, the data will be frozen and retained indefinitely by Medtronic. Data collection requirements are summarized in Table 6 below.

Table 6: Data collection and study procedure requirements at subject visits

	Ablation Procedure				Repeat Ablation Procedure (1-180 days)				30 day	3 month	6 month	Unscheduled
	Baseline	Procedure	Post-procedure	Discharge	Baseline	Procedure	Post-procedure	Discharge				
Consent	X											
Incl/Excl Criteria	X											
History	X											
Physical exam	X(11)			X	X			X	X	X	X	X
Pregnancy Screen (if applicable per local requirement)	X											
Standard neurologic evaluation (performed by neurologist)	X			X	X			X	X	X(10)	X(10)	X
Concomitant medications	X		X	X	X			X	X	X	X	X
Arrhythmic Sx review	X				X				X	X	X	X
12 lead ECG	X(11)			X	X			X	X	X	X	X
Cardioversion log	X				X				X	X	X	X
TTE	X(2)				X(2)							
Esophageal visualization		X				X						
MRI or CT for PVS	X(3, 11)									X(3)		
██████████		████		████					████			
NIHSS (performed by neurologist)				X(1)				X(1)	X(1)	X(1)	X(1)	X(1)
MMSE (performed by neurologist)	X			X(1)				X(1)	X(1)	X(1)	X(1)	X(1)
mRS (performed by neurologist)				X(1)				X(1)	X(1)	X(1)	X(1)	X(1)
INR	X	X	X	X	X	X	X	X	X	X	X	X
ACT		X				X						
48 hour ambulatory ECG monitoring	X(11)										X	
TEE		X(5)				X(5)						
AE review		X	X	X	X	X	X	X	X	X	X	X
GENius Data File Collection		X				X						

1. Only for subjects diagnosed with protocol defined stroke
2. Not required for repeat ablation procedures as long as last TTE was performed within 6 months of reablation procedure
3. Only required for the subset subjects in the PVS assessment cohort. The same technology should be used for baseline and 3 month scans

5. Required 48 hours prior to ablation procedure

10. Only for subjects that have been diagnosed with a focal or global neurological deficit and/or signs/symptoms suggestive of stroke
11. Must be completed within 3 months prior to index ablation procedure

7.6 Subject visit schedule

After receiving notice of ablation procedure, Medtronic will provide the target dates and windows for each visit to the investigational center and if subject is to be included in the PVS subset. Should a subject visit fall outside the pre-specified window, a study deviation must be reported and the original follow-up schedule maintained for subsequent visits. Data analyses include late follow-up visits. Therefore, a late visit is preferred over a missed visit, but must be accompanied by a deviation.

The follow-up schedule will be reset for subjects that require a reablation procedure with the Phased RF system. For example, if subjects had reablation procedures after their 30-day follow-up visits, new target dates will be generated for their new 30-day follow-up visits and revised target dates for their 3-month and 6-month post-ablation visits.

Table 7: Visit Windows

Study Follow-up Visit	Window (Calculated calendar days post-ablation from the subjects last ablation procedure)		
	Window Start (days post-procedure)	Target (days post-procedure)	Window End (days post-procedure)
Procedure	0	0	0
Discharge	1	1	7*
30 Day	30	30	37
3 Month	76	90	104
6 Month	180	180	210**

[REDACTED]

****6-month ambulatory ECG monitoring must occur within the 6-month visit window. Subjects discontinuing Amiodarone at the 3-month visit should not start their 6-month ambulatory ECG monitor until at least 90 days following Amiodarone discontinuation.**

7.7 Study procedure details

Physical Exam: Conduct a complete physical exam including but not limited to height, weight, arrhythmic history and cardiovascular history. For index Baseline visit, the exam should be completed within the 3 months prior to the ablation procedure.

Pregnancy Screen: If the subject is a female of child-bearing potential, a serum or urine pregnancy test must be performed. If not of child-bearing potential, make sure there is documentation in subject's medical record to indicate this.

Neurologic Evaluation: The site neurologist will conduct a standard neurologic exam on all subjects to determine if focal or global neurological deficit or other neurological signs/symptoms consistent with stroke are present at the time of the study visit.

The Baseline neurologic evaluation may be completed within the 2 weeks prior to the index ablation procedure.

Upon the sites' awareness of Unscheduled visits, the neurologic evaluation conducted by the site neurologist should be completed as soon as possible.

National Institute of Health Stroke Scale (NIHSS): The site neurologist will administer the NIHSS to subjects that have been identified to have focal or global neurological deficit or other neurological signs/symptoms consistent with stroke at the time the deficit or symptoms present and all subsequent study follow up visits.

Mini-Mental State Exam (MMSE): The site neurologist will administer the MMSE to all subjects at the baseline visit.

In addition, the site neurologist will administer the MMSE for the following:

- [REDACTED]
- Subjects that have been identified to have post-ablation focal or global neurological deficit (or other neurological signs/symptoms consistent with stroke) at the time the deficit or symptoms present and all subsequent study follow up visits.

Modified Rankin Score (mRS): The site neurologist will administer the mRS to subjects that have been identified to have focal or global neurological deficit (or other

neurological signs/symptoms consistent with stroke) at the time the deficit or symptoms present and all subsequent study follow up visits.

Concomitant Medications: All prescribed cardiovascular and vitamin K antagonist medications and dosages will be collected at protocol defined study visits and unscheduled study visits.

For purposes of the study, cardiovascular medications are defined as the following major types of cardiovascular medications per American Heart Association (AHA):

- Anticoagulants
- Antiplatelet agents
- Angiotensin-converting enzyme (ACE) inhibitors
- Angiotensin-II receptor blockers (or inhibitors), also known as ARBs
- Antiarrhythmic drugs (AADs)
- Beta blockers
- Calcium channel blockers
- Diuretics
- Vasodilators
- Digitalis preparations
- Statins

Therapeutic anticoagulation: Therapeutic anticoagulation is defined as an INR of 2.0 to 3.5. All subjects are required to be prescribed to a vitamin K antagonist (VKA) 30 days prior to the ablation procedure to achieve therapeutic anticoagulation. Subjects will then be required to stay on a VKA for the remainder of their study participation.

Antiarrhythmic Drug (Class I and III) and Direct Cardioversion Use: All subjects will be allowed to be prescribed to one or more class I and/or III antiarrhythmic drug and undergo direct cardioversion as described in Table 8 below.

Table 8: Class I and III Antiarrhythmic Drug Use Intervals

AAD & DC Cardioversion	Use Intervals	
Amiodarone	Allowed; Baseline to 3 month visit	Not allowed within 90 days prior to 6-month Holter *
Class I and III AADs	Allowed; Baseline – 4 months	Not allowed within 60 days prior to 6-month Holter*
DC cardioversions	Allowed; Baseline – 4 months	Not allowed within 60 days prior to 6-month Holter*

*For patient safety and welfare, investigators are allowed to prescribe the use of AAD or DC Cardioversions if medically necessary during “not allowed” use intervals. However, this will be considered a protocol deviation.

History of Atrial Fibrillation: At the time of enrollment, the investigators are required to indicate in the subjects' medical record whether the existing atrial fibrillation is persistent or long-standing persistent as defined in the inclusion criteria. In addition, the subject will be required to complete a 48-hour ambulatory ECG monitor at the baseline visit to demonstrate persistent AF at the time of enrollment.

Arrhythmic symptom review: Subjects will be queried to determine what symptoms if any, they are experiencing due to atrial fibrillation at protocol defined clinic visits and unscheduled clinic visits.

12 Lead ECG: Will be collected at protocol defined study visits and unscheduled study visits to determine heart rhythm along with specific intervals. The Baseline 12 lead ECG should be completed within the 3 months prior to the index ablation procedure.

Cardioversion Log: At protocol defined study visits and unscheduled study visits the cardioversion log will be updated with the date of any electrical cardioversions that have been performed since last clinic visit.

48-hour ambulatory ECG monitor: Will be collected at protocol defined study visits to determine heart rhythm. Examples of ambulatory ECG monitors are Holter monitors, wearable wireless adhesive ECG monitors (e.g. ECG patch monitors).

For the Baseline ambulatory ECG monitoring, this should be completed within the 3 months prior to the index ablation procedure to document study subject has continuous AF. Subjects may be asked to repeat an ambulatory ECG monitoring session if less than 24 hours of analyzable monitoring time is obtained or continuous AF is not demonstrated. The ambulatory ECG monitoring technology used at the 6-month visit should be the same as the technology used at the baseline visit.

Trans-thoracic echocardiogram (TTE): Will be collected at Baseline or within previous 6 months of the index or reablation procedure to determine atrial volume and size.

Trans-esophageal echocardiogram (TEE): Will be collected within 48 hours prior to the index or reablation procedure to rule-out left atrial thrombus.

If a left atrial thrombus is visualized during pre-procedure TEE, the study subject will not undergo the study ablation procedure at that time.

MRI/CT scan (Chest): Will be done prior to ablation procedure and 3 months post index ablation procedure for the assessment of PVS in subjects in the PVS assessment cohort.

For the Baseline scan, this should be completed within the 3 months prior to the index ablation procedure.

The imaging technology (MRI, CT) used at Baseline pre-procedure scan must match the 3-Month post-procedure scan technology for a given study subject.

International normalized ratio (INR): Blood will be drawn at each study visit (i.e. within the study visit window) to determine the subject's INR.

Two (2) INR levels demonstrating the study subject is therapeutic on VKA are required in the 30 days prior to the index ablation procedure. INR draws from other health care providers are permitted.

Esophagus visualization: Perform visualization prior to ablation procedure using site standard procedure.

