6.2 Study objectives

6.2.1 Primary safety objective

Demonstrate that the observed incidence of procedure and/or device related incidence of new stroke (excludes transient ischemic attack) within 30 days of an ablation procedure (index or reablation) with the Phased RF System is less than 1.8% with observed upper confidence boundary that is less than 3.5%.

The definition of stroke is provided in the Table below. To meet the primary endpoint an event must meet all of the criteria in Table 5 below as determined by the clinical events committee (CEC).

Table 5: Protocol defined stroke

Definition	Hemorrhagic and Ischemic stroke with rapid onset of a focal or global neurological deficit or other neurological signs/symptoms consistent with stroke
Symptom duration	Duration of focal or global neurological deficit ≥ 24 hours; OR Duration of focal or global neurological deficit < 24 hours IF : 
 • Therapeutic interventions 
 ○ Thrombolytic therapy ○ Intracranial angioplasty OR • Neuroimaging documents a new hemorrhage or ischemic infarct OR • Neurological deficit results in death
Periprocedural definition	Within 30 days of Phased RF ablation procedure where the investigational catheter was placed in the left atrium
Diagnosis	Appropriate diagnostics will be determined by the site's neurologist's clinical evaluation and include one or more of the following: 
 • Clinical signs and symptoms consistent with focal or global neurologic deficit • Neuroimaging procedure (CT or MR scan or cerebral angiography) • Lumbar puncture (i.e. subarachnoid hemorrhage) AND Adjudicated as peri-procedural stroke by clinical events committee

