7.10 Discharge follow-up

- Physical Exam
- Neurologic evaluation
 - It is strongly recommended that the neurological evaluation be conducted after the effects of anesthesia subside
 - If evaluation identifies focal or global neurological deficit and/or signs/symptoms suggestive of stroke; then the following assessments are required:
 - NIHSS
 - MMSE
 - mRS
- 12 lead ECG
- Review of arrhythmic symptoms
- INR*
- Concomitant medications

***NOTE: subject cannot be discharged until INR is greater than or equal to 2.0 as per the HRS Consensus statement (After removal of all sheaths, warfarin should be reinitiated within four to six hours, and low-molecular weight heparin (LMWH) (enoxaparin 0.5–1.0 mg/kg twice daily) or intravenous heparin should be used as a bridge to resumption of INR 2.0–3.0).**

7.11 30 day follow-up

NOTE: 30 day follow up visit should occur as close to day 30 following the ablation procedure without occurring prior to day 30.

- Physical Exam
- Neurologic evaluation
 - If evaluation identifies focal or global neurological deficit and/or signs/symptoms suggestive of stroke; then the following assessments are required:
 - NIHSS
 - MMSE
 - mRS
- 12 lead ECG
- Review of arrhythmic symptoms
- INR
- Concomitant medications
- [REDACTED]
- [REDACTED]
- Cardioversion history

7.12 3 month follow-up

- Physical Exam
- Neurologic evaluation and assessments for subjects previously diagnosed with a focal or global neurological deficit and/or signs/symptoms suggestive of stroke; assessments include:
 - NIHSS
 - MMSE
 - mRS
- 12 lead ECG
- Review of arrhythmic symptoms
- INR
- Concomitant medications (amiodarone required to be stopped at this visit)
- Cardioversion history
- MRI or CT scan (Chest) for subjects in the PVS assessment cohort; subjects randomized to the PVS assessment cohort will receive a 3-month CT or MRI scan at their first 3-month post-ablation visit (e.g. if a subject is reablated after the initial 3-month post-ablation visit, a second CT scan for PVS screening is not required at the 3-month post-reablation visit). The same scanning technology should be used for the baseline and 3 month PVS assessment.
- [REDACTED]

7.13 6 month follow-up

- Physical Exam
- Neurologic evaluation and assessments for subjects previously diagnosed with a focal or global neurological deficit and/or signs/symptoms suggestive of stroke; assessments include:
 - NIHSS
 - MMSE
 - mRS
- 12 lead ECG

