7.14 Unscheduled follow-up visits

An unscheduled visit is defined as any unplanned office visit at the study site that occurs between protocol required visits. The requirements at an unscheduled visit are:

- Physical Exam
- Neurologic evaluation
 - If evaluation identifies focal or global neurological deficit and/or signs/symptoms suggestive of stroke; then the following assessments are required:
 - NIHSS
 - MMSE
 - mRS
- 12 lead ECG
- Review of arrhythmic symptoms
- INR
- Concomitant medications
- Cardioversion history

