12.2.3 Definition of procedure and/or device related stroke

Procedure and/or device related strokes are defined as events classified by the CEC meeting all of the requirements in Table 5. Specifically, the stroke must have a symptom onset date within 30 days of an ablation procedure where at least one phased RF catheter is deployed into the left atrium and be considered related to the procedure and/or device by the CEC.

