12.2.4 Rationale for stroke threshold

The peri-procedural stroke rate is not well characterized in the persistent and long-standing persistent AF population. The observed procedure or device related stroke rate among the 176 ablated subjects in the TTOP-AF study was

2.8% with an upper one-sided 95% confidence interval of 5.9%. However, the FDA Center for Devices and Radiological Health's cardiac devices advisory panel indicated that both the observed stroke rate and its associated upper confidence boundary in the TTOP-AF study were too high to enable approval of the phased RF ablation system. Medtronic has identified several mitigation strategies that are expected to lower the peri-procedural stroke rate. With these mitigation strategies enforced in the current protocol, Medtronic believes the true procedure and/or device related peri-procedural stroke rate will be less than 1.8%, a value similar to the peri-procedural stroke rates reported in recent observational studies.

Specifically, a single site registry study by Patel et al., reported a 1.8% per-procedural stroke rate (one-sided upper 95% CI: 2.6%) among 1209 subjects with persistent or long-standing persistent AF undergoing off label AF ablation. Additionally, Patel et al. found that persistent AF was the only independent predictor of peri-procedural stroke risk in a multivariable analysis. A similar study was performed by Spragg et al, evaluating 517 subjects with atrial fibrillation. The stroke rate was 1.7% (95% one-sided UCB; 3.8%) for the 240 subjects with persistent atrial fibrillation. A key limitation with these observational trials is that the studies' did not require rigorous follow-up protocols and therefore the stroke rates may be under reported.

After considering all available data sources together with close consultation with the FDA, a procedure and/or device related peri-procedural stroke threshold of 3.5% was chosen. This threshold is greater than the upper one-sided 95% confidence intervals reported by Spragg et al and Patel et al but is lower than the upper confidence interval for the peri-procedural stroke rate observed in the TTOP-AF study. Additionally, a peri-procedural stroke threshold of 3.5% mandates that the observed study stroke rate must be less than 1.8% for study success for a sample size of at least 300 ablated subjects.

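### The 30-day neurologic evaluation looks only at the visit day, so a stroke that clears between discharge and day 30 without a study-site visit depends on general adverse event review

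*Protocol*

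**What the plan says.** **Endpoint.** Protocol section 12.2.3 states that "the stroke must have a symptom onset date within 30 days of an ablation procedure where at least one phased RF catheter is deployed", and the Clinical Events Committee (CEC) must also judge the stroke related. In Table 5 (section 6.2.1) the main duration criterion is "Duration of focal or global neurological deficit ≥ 24 hours". A shorter deficit counts only with thrombolysis or intracranial angioplasty, a new lesion on imaging, or death. Neither place requires the deficit to persist until a visit.

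**Examination.** Section 7.7 gives the purpose of the neurologist's evaluation as "to determine if focal or global neurological deficit or other neurological signs/symptoms consistent with stroke are present at the time of the study visit".

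**Timing.** Table 7 puts the discharge visit at day 1–7 and the 30-day visit at day 30–37. Section 7.11 adds that the "30 day follow up visit should occur as close to day 30 following the ablation procedure without occurring prior to day 30". At 3 and 6 months the evaluation is only for subjects already found to have a deficit or suggestive signs (Table 6, footnote 10).

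**Other routes.** Section 7.14 requires a neurologic evaluation at unscheduled visits: "An unscheduled visit is defined as any unplanned office visit at the study site that occurs between protocol required visits". For those visits section 7.7 says that "the neurologic evaluation conducted by the site neurologist should be completed as soon as possible". Adverse events are collected from enrolment onward (section 10.1), and Table 6 marks adverse event review at every post-procedure visit. The CEC tests each reported event against Table 5 (section 10.3).

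**The concern.** The endpoint covers a 30-day period, but the examination meant to find it is described as a snapshot. Take a subject with two days of arm weakness around day 10 who has recovered by day 30 and did not come to the study site. The day-30 evaluation, done as section 7.7 describes it, can be normal. The NIHSS, the mRS and the post-baseline MMSE follow from a deficit or symptoms already identified, so in the visible text they do not screen. The symptom review in section 7.7 asks about atrial fibrillation symptoms. The same section asks for cardioversions since the last clinic visit, so the protocol writes a look-back for cardioversions but not for its primary endpoint.

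A missed stroke leaves the subject in the denominator as a non-event. The tipping-point analyses in section 12.2.8 address subjects who leave the study early, not a subject who attends day 30 with an unreported event. In a single-arm study against a fixed goal, the error moves the result in one direction only, towards success.

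**Working it through.** **1. Which strokes depend on the gap**

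| Stroke after ablation | Route to detection in the visible text |
|---|---|
| Deficit present at the discharge or 30-day visit | Scheduled neurologist evaluation |
| Deficit present at an unscheduled study-site visit | Neurologist evaluation under 7.7 and 7.14 |
| Deficit under 24 hours that qualifies through treatment, imaging or death | Implies medical contact or death, so adverse event reporting is to be expected, then the CEC |
| Deficit of at least 24 hours after discharge, cleared before day 30, no unscheduled study-site visit | General adverse event review only, then the CEC if reported |

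Only the last row is the gap. Within the 30-day period it can extend over 30 − 7 = 23 days if the discharge evaluation is on day 7, or 30 − 1 = 29 days if it is on day 1.

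**2. The plan's own figures** (Protocol 12.2.6 and SAP 3.2.4)

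Inputs: n = 300; one-sided exact test at 0.05; performance goal 3.5%; observed rate below 1.8%.

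The exact one-sided 95% upper limit for x events is the 0.95 quantile of Beta(x + 1, n − x).

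- x = 5: 5/300 = 1.67%, upper limit 3.47%. Both conditions are met.
- x = 6: 6/300 = 2.00%, upper limit 3.91%. Both conditions fail.

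The rule is therefore to pass with at most 5 strokes, and P(pass) = P(X ≤ 5) with X ~ Binomial(300, p).

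| True rate p | P(pass), recomputed | Stated |
|---|---|---|
| 1.0% | 91.7% | 90% |
| 1.3% | 80.2% | 80% |
| 1.8% | 54.6% | 55% |
| 3.5% | 4.76% | below 5% |

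The stated figures reproduce. All of them assume that every qualifying stroke is found.

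**3. What incomplete capture would do**

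Let m be the share of all qualifying strokes that no route captures. Replace p by p(1 − m). At a true rate of 3.5%:

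| Assumed m | Effective rate | P(pass) |
|---|---|---|
| 0 | 3.500% | 4.8% |
| 2% | 3.430% | 5.4% |
| 5% | 3.325% | 6.5% |
| 10% | 3.150% | 8.7% |

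P(pass) crosses 5% at m of about 0.8%, because the design starts at 4.76%. The documents give no value for m, so these rows are a what-if and not an estimate.

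**The case against.** The strongest reply is that several other routes are mandatory. A two-day deficit on day 10 is a new adverse event that has to be recorded, adverse event review is marked at the 30-day visit, and the CEC must test each event against Table 5. Unscheduled visits bring the same neurologist evaluation. The trigger for the scales in section 7.11 carries no visit-day limit, and the physical examination, as section 7.7 defines it, includes cardiovascular history. Nor does Table 5 require any scale score for an event to count. All of this stands, and it narrows the gap to the last row of the first table. It does not close it: none of these steps, as written, asks about stroke symptoms since the previous evaluation, and the CEC can judge only what is reported.

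A reader might infer that a stroke resolving before day 30 goes unfound, or that this evaluation is the only stroke-specific step. The documents support neither. The other routes can find such a stroke. Redactions in Table 6 (a row marked at procedure, discharge and 30 days), in the MMSE paragraph of 7.7 and in the list in 7.11 mean that the absence of another stroke-specific step can be stated for the visible text only.

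A reader might also take the what-if as the effect of this wording. It is not: m applies to all qualifying strokes, and the gap concerns only some of them. Sensitivity to one event is a feature of any threshold rule and does not show that strokes will be missed.

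Section 12.2.4 says that the comparator studies "did not require rigorous follow-up protocols and therefore the stroke rates may be under reported". That is a remark about follow-up in general. This protocol does more, with neurologist evaluations and central adjudication, so the remark is a reason to ask for complete capture here and not evidence of the same failing.

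**Conclusion.** The point holds in this limited form. The wording of section 7.7 leaves one kind of qualifying stroke to a general adverse event review with no stroke prompt: a deficit of at least 24 hours that clears before day 30 in a subject who made no unscheduled study-site visit. The direction of any resulting error is certain, since a miss can only help the study pass. Its size is unknown. What can be said is that a single miss would turn 6 of 300 into 5 of 300 and reverse the conclusion, and that the stated type I error below 5% has almost no room for incomplete capture. The calculation assumes exactly 300 evaluable subjects and an equal, independent chance of missing each stroke. This is a cheap improvement in ascertainment. It is not a defect in the test or the sample size, and no stated figure needs to change.

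**What to change.** In section 7.7, widen the purpose of the evaluation to cover deficits or symptoms present at the study visit or at any time since the previous neurologic evaluation. At the 30-day neurologist visit, and at the repeat-ablation baseline and unscheduled evaluations, add a short fixed set of stroke-symptom questions for that interval. Record any positive answer as a neurologic adverse event for CEC review. Mirror the change in 7.11, 7.14 and the neurologic evaluation row of Table 6, and name adverse event review in the 7.11 list if the redacted items do not already do so.

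The cost is protocol and case report form wording, a few minutes in visits that already take place, and some additional non-stroke reports for the CEC.
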